1.3.2. Secondary Endpoints

- Change from Baseline in caudate volume as assessed via vMRI at Month 12 (key secondary)
- Change from Baseline in cUHDRS scores at Month 12
- Change from Baseline in blood tHTT protein at Month 12
- Change from Baseline in CSF mHTT protein at Month 12
- Change from Baseline in blood mHTT protein at Month 12

1.3.3. Exploratory Endpoints

- Change from Baseline in CSF mHTT protein at Month 3
- Change from Baseline in blood mHTT protein at Month 3
- Change from Baseline in whole brain, putamen, and, ventricular volume (as assessed by vMRI) at Month 12
- Change from Baseline in Unified Huntington's Disease Rating Scale (UHDRS) TFC sub-score at Month 12
- Change from Baseline in other UHDRS sub-scores including Total Motor Score (TMS), Symbol Digit Modalities Test (SDMT), and Independence Scale (IS) at Month 12
- Change from Baseline in the short form of the Problem Behaviors Assessment (PBA-s) (substituting for the UHDRS Behavioral Examination) at Month 12
- Change from Baseline in wearable accelerometer assessment Timed Up and Go (TUG), 2-minute walk distance, and postural sway at Month 12
- Change from Baseline in the Functional Rating Scale (FuRST) 2.0 questionnaire at Month 12
- Change over time in blood *HTT* mRNA
- Change over time in plasma and CSF neurofilament light chain (NfL)

1.3.4. Pharmacokinetic Endpoints

- Plasma trough concentration (C_{trough}) and accumulation ratio of PTC518 in plasma over time and accumulation ratio of PTC518 in CSF at Visits 5 through 8

1.3.5. Safety Endpoints

- Safety profile as characterized by treatment-emergent adverse events (TEAEs), laboratory abnormalities, NfL levels in plasma and CSF, electrocardiograms (ECG), vital signs, [REDACTED]
Columbia Suicide Severity Rating Scale (C-SSRS), and physical examination

1.4. Sample Size

The sample size calculation for each disease stage is based on mean change from baseline in blood tHTT protein at Month 3 (primary endpoint) assuming PTC518 has the same effect on blood tHTT protein reduction. With an effect size of 0.85 (i.e., the magnitude of treatment difference is 85% of one standard deviation [SD]), achievement of 85% power at 2-sided alpha level 0.05 would require 24 subjects. Approximately 24 subjects will be randomized to each active treatment arm and approximately 36 additional subjects per disease stage will be randomized to placebo. An additional 18 subjects (per disease stage) may be randomized to the maximum tolerated dose. Up to 252 adult male and female subjects (126 per disease stage) will be enrolled.

1.5. Randomization and Blinding

After subjects complete all baseline procedures on Day 1 and are eligible to be randomized, the site staff will utilize an Interactive Response Technology (IRT) system to assign study medication to each subject. Subjects will first be randomized to Parts A or B or Parts D or E in a 1:1 ratio, depending on their HD-ISS staging criteria after which they will be randomized to active treatment or placebo within each part in a 2:1 ratio of active to matching placebo. As specified in the DSMB Charter, a DSMB will undertake an unblinded review of safety data from the 5 and 10 mg dosing groups and provide recommendations on when Parts C and F, with a 20 mg active treatment arm, can be initiated at that time, subjects will be randomized to any study Part that is currently open for enrollment, and then to either active treatment or placebo (in a 2:1 ratio) within that Part.

Enrollment for the Stage 2 group will be stratified by PIN_{HD} score, with the following stratification classes:

- 0.180-0.679
- 0.680-1.520
- 1.521-4.930

Enrollment for the Mild Stage 3 group will be stratified by TFC score, with the following stratification classes:

- 11
- 12

- 13

The randomization code will be kept strictly confidential and accessible only to the unblinded study statistician who is not directly involved in the conduct of the study. The study will be performed in a double-blind fashion. The investigator and study staff (including processing laboratory personnel), the subjects, and the staff of PTC Therapeutics (PTC) will remain blinded to the treatment until after the database is locked.

2. SUBJECT POPULATIONS FOR ANALYSIS

2.1. Intent-to-Treat (ITT) Population

The ITT population will include all randomized subjects who take at least one dose of the study drug. This ITT Population will be utilized for all efficacy analyses, with subjects analyzed according to their assigned randomized treatment.

2.2. Per Protocol (PP) Population

The PP population will include all subjects in the ITT population who have no major protocol deviations that affect the validity of the efficacy measurements. The PP population will be used for sensitivity analysis of the primary efficacy endpoint. The criteria for inclusion in the PP population will be finalized prior to the database lock for the double-blind treatment period and the study unblinding. Subjects who meet the following criteria, but not limited to, will be excluded from the PP population:

- Had significant inclusion or exclusion criteria violations
- Received study treatment different from the randomized treatment throughout the first 3 months of study
- Had major protocol deviations which may impact the assessment for efficacy of study treatment
- Unblinded due to the partial clinical hold by the FDA

A separate documentation containing the final exclusion criteria and a list of subjects in this population will be finalized before the database lock for the double-blind treatment period and the treatment unblinding.

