9.1. Subject Populations for Analysis

Intent-to-Treat (ITT) Population: All randomized subjects who take at least 1 dose of study drug. The ITT Population will be used in all efficacy analysis and subjects will be analyzed according to their randomized treatment.

Per Protocol (PP) Population: All subjects in the ITT population who have no major protocol deviations that affect the validity of the efficacy measurements. The PP Population will be used for sensitivity analysis of the efficacy endpoint. The criteria for inclusion in the PP Analysis Set will be finalized prior to study unblinding and detailed in the SAP.

Safety Population: All randomized subjects who receive at least 1 dose of study drug, with subjects grouped according to the treatment they actually receive. The Safety Population will be used in all safety analyses.

PK Population: All randomized subjects who take at least 1 dose of study drug. This analysis set comprises all subjects included in the Safety Population who did not violate the protocol in a way that might affect the evaluation of the effect of the study drug(s) on the PK assessment (ie, without major protocol violations or deviations).

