3.3. Interim Analysis

An interim analysis was conducted in June 2023 to confirm the PK and PD expectations and to evaluate safety after approximately 36 subjects in Stage 2 have completed 12 weeks of treatment. Subsequently, in June 2024, an update of interim analysis was conducted when these subjects completed 12 months of treatment. The interim analyses included only descriptive summaries of PK, PD, clinical efficacy and safety endpoints. Since the interim analyses followed the same procedures as the DSMB, the analysis details were outlined in the DSMB SAP.

An independent analysis team conducted the unblinded analysis. Only summary level results were shared with the PTC study team. The study has maintained double-blinding for investigators and the sponsor study team at a subject level until after the database is locked.

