5.2. Sensitivity Analysis

5.2.1. Sensitivity Analysis on PP Population

The above MMRM model for the primary endpoint will also be performed on the PP Population. The blood tHTT protein and percent change from baseline will be summarized descriptively by treatment group for each visit.

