5.3. Secondary Endpoints Analysis

Key Secondary Endpoint Analysis

The percent change from baseline in caudate volume as assessed via vMRI at Month 12 is the key secondary endpoint.

A MMRM model will be used to compare each PTC518 dose group with placebo group for the percent change from baseline in caudate volume as assessed via vMRI at Month 12. The response variable is the percent change from baseline in caudate volume. The model will include fixed effects for treatment, disease stage (by PINHD bin for Stage 2 only and by TFC for Mild Stage 3 only) with baseline caudate volume as a covariate. The time and time by treatment interactions will be included in the model where time is defined as: date of caudate assessment – date of randomization + 1. The intercept and time of collection will be included as a random effect nested within subjects.

The unstructured covariance matrix will be used in the model. If the model does not converge under the unstructured covariance matrix, the Variance Component covariance matrix will be used/. If the model still does not converge, the random effect will be excluded. The treatment effect and treatment difference will be estimated by the LS means and the difference in LS means, along with their SE and with 95% CIs, and the nominal p-values (2-sided) for each pairwise comparison (PTC518 vs. placebo) will be provided.

The caudate volume (left, right, and total [left + right]) and percent change from baseline will be summarized descriptively by treatment group for each visit.

Other Secondary Endpoints Analysis

Other secondary endpoints include:

- Change from baseline in cUHDRS scores at Month 12

An ANCOVA model will be performed to compare each dose group with placebo group for the change from baseline in cUHDRS at Month 12. The model will include treatment group as the independent variable and baseline cUHDRS, disease stage, CAG, age, CAG by age interaction as covariates. The treatment effect and treatment difference will be estimated by the LS means and the difference in LS means, along with their SE and with 95% CIs, and the nominal p-values (2-sided) for each pairwise comparison (PTC518 vs. placebo) will be provided.

- Change from baseline in blood tHTT protein at Month 12

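### Hold-unblinded subjects are excluded only from the per-protocol run on blood tHTT; no planned analysis removes or flags Month 12 cUHDRS ratings made after unblinding

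*SAP*

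**What the plan says.** **The exclusion.** SAP 2.2 names one group for removal from the PP population as "Unblinded due to the partial clinical hold by the FDA". The same section fixes what that population is for: "The PP population will be used for sensitivity analysis of the primary efficacy endpoint". SAP 5.2.1 carries this out for blood tHTT alone: "The above MMRM model for the primary endpoint will also be performed on the PP Population". Protocol 9.1 is looser ("The PP Population will be used for sensitivity analysis of the efficacy endpoint"), but neither document specifies a PP analysis of cUHDRS.

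**The cUHDRS.** SAP 2.1 sets the population: "This ITT Population will be utilized for all efficacy analyses, with subjects analyzed according to their assigned randomized treatment". SAP 5.3 gives a single model: "An ANCOVA model will be performed to compare each dose group with placebo group for the change from baseline in cUHDRS at Month 12". In SAP Table 1 the only intercurrent event for cUHDRS is treatment discontinuation, with data later than 30 days after the last dose excluded. Unblinding is not listed. The subgroups in SAP 5.6 are disease-stage classes only.

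**The blind.** SAP 1.5 says that investigators, study staff, subjects and sponsor staff stay blinded until database lock. Protocol 5.4 allows unblinding only for subject emergencies or at the end of the study. SAP 3.3, in its account of the interim analyses, adds: "The study has maintained double-blinding for investigators and the sponsor study team at a subject level". The hold is mentioned nowhere in either document except in the SAP 2.2 list.

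**The concern.** The sponsor has judged hold-related unblinding serious enough to take subjects out of an analysis, but has applied that judgement to the endpoint least open to it. Knowing the assignment should hardly affect a blood protein measured in a laboratory. It can affect a motor rating or a functional-capacity rating, and both enter the cUHDRS.

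At stake is how a cUHDRS difference would be read. If some Month 12 ratings were made with treatment known, a reader of the report could not tell how far the difference depends on them, because no planned analysis separates them.

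**Working it through.** **1. The plan's own figure.** The only power statement is for blood tHTT (SAP 1.4): effect size 0.85, 85% power, two-sided 0.05, 24 subjects. Per arm, 2 × ((1.960 + 1.036)/0.85)² = 24.85, so the stated 24 is close. No power figure is given for cUHDRS, and the point does not depend on this calculation.

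**2. Which analyses remove hold-unblinded subjects.**

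| Endpoint | Main analysis | Run without them |
|---|---|---|
| Blood tHTT, Month 3 | ITT MMRM | Yes, PP (SAP 5.2.1) |
| cUHDRS, Month 12 | ITT ANCOVA | None |

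**3. Who can still contribute a post-unblinding rating.** SAP Table 2 opens the Month 12 window on Day 331 and closes it 30 days after the last dose. A value can fall in it only if last dose + 30 ≥ 331, that is, last dose on or after Day 301. Earlier stoppers are already out of the ANCOVA, whether or not they were unblinded. The exposed group is therefore subjects unblinded before their Month 12 rating with a last dose on or after about Day 301.

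**4. Whether an earlier cUHDRS could serve as a check.** The cUHDRS needs Stroop Word Reading (SAP 3.4.4). The protocol's Schedule of Assessments collects only the SDMT from the cognitive battery at Visits 3 to 7. On schedule, then, the cUHDRS exists only at Baseline and Month 12, and no scheduled intermediate value can act as a blinded comparison.

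**5. How much judgement the score carries.** From the formula in SAP 3.4.4, one TFC point moves the cUHDRS by 1/1.9 = 0.53 and one TMS point by 1/14.9 = 0.067. One TFC point plus three TMS points is 0.53 + 0.20 = 0.73.

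**6. Illustration of size (assumed inputs).** Parts A, B, D and E take about 144 subjects at 2:1, so 48 per dose and 48 on placebo. The standard error of a difference is √(2/48) = 0.204 SD. Let f be the share of active-arm Month 12 ratings made with treatment known and s the shift in those ratings, in SD. Bias = f × s. With no true effect, the two-sided rejection rate is P(|Z + bias/0.204| > 1.96).

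| f | s | Bias (SD) | Rejection rate |
|---|---|---|---|
| 5% | 0.25 | 0.013 | 5.0% |
| 10% | 0.5 | 0.05 | 5.7% |
| 20% | 0.5 | 0.10 | 7.8% |
| 30% | 0.5 | 0.15 | 11.4% |
| 30% | 1.0 | 0.30 | 31.2% |

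If both arms shift equally in opposite directions, bias = 2 × f × s. For f of 5–30% and s of 0.2–0.4, that is 0.02 to 0.24 SD. A bias of 0.02 gives about 5.1%, and 0.12 gives about 9%.

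**7. Precision of a supportive run.** The detectable difference at 80% power is (1.960 + 0.842) × √(2/n). With 48 per arm it is 0.57 SD. It is 0.60 SD if 10% are removed from each arm (n = 43.2) and 0.68 SD if 30% are removed (n = 33.6).

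**The case against.** The strongest reply is that no harm is shown. The hold appears in one line. The documents do not say who learned the assignment, how many subjects were affected, when, or whether they continued dosing. If dosing ended at unblinding, the window in step 3 may leave few affected ratings or none. This stands as a limit on size. It does not close the gap, because the cut-off follows the last dose and not the unblinding date.

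Several further points also stand:

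- The whole cUHDRS is not rater-judged. SDMT and Stroop Word Reading are timed counts of correct answers. A subject's own knowledge of treatment might affect effort, but the examiner does not rate them.
- Secondary endpoints carry no multiplicity adjustment (SAP 3.4.7) and cUHDRS p-values are nominal, so a shifted rejection rate breaks no controlled error rate.
- SAP 4.2 already provides counts per population and a listing of excluded subjects, so part of the disclosure is planned.

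A reader might infer that SAP 3.3 flatly contradicts SAP 2.2. The documents do not support that as it stands. The sentences just before it describe an independent team sharing only summary results, so it can be read as saying that the interim looks did not break the blind. The broader statements that do not sit with SAP 2.2 are those in SAP 1.5 and protocol 5.4.

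**Conclusion.** The point holds in limited form. The plan removes hold-unblinded subjects from a sensitivity analysis of a blood assay and has no counterpart for the one clinical secondary endpoint. Exposure is confined to subjects unblinded before their Month 12 rating whose last dose was on or after about Day 301.

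The size of any bias cannot be derived from the documents. A reader might take the 9% rejection rate, or the larger ones in the working, as an estimate for this trial. They are not: every share and shift is assumed, and at the low end the rate stays at about 5%. A reader might also infer that cUHDRS ratings were in fact biased. Nothing in the documents shows that any Month 12 rating followed unblinding. The case for acting is that the plan would not reveal it if one had, and that finding out costs little.

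**What to change.** 1. In SAP 5.3, add one supportive cUHDRS ANCOVA with the same model, excluding Month 12 values assessed on or after the subject's unblinding date. Keep the ITT analysis as the main one.
2. Tabulate hold-unblinded subjects by arm, by unblinding date relative to the Month 12 rating, and by who was unblinded (subject, site staff or rater, sponsor). If no Month 12 rating followed unblinding, the table shows it and the supportive run equals the main one.
3. Reconcile SAP 1.5 and protocol 5.4 with SAP 2.2, and clarify whether the SAP 3.3 sentence refers only to the interim analyses.

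The descriptive summaries in SAP 5.4 need no matching change.

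**Cost.** SAP wording, one table and one model run. The PP list already requires these subjects to be identified, but the documents do not say that unblinding dates are recorded, so they may have to be retrieved. The supportive run has fewer observations, with the loss of precision shown in step 7. It is a complete-case analysis and could carry selection bias if unblinding differed by arm or prognosis, so it should be read only alongside the ITT result.

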2.3. Safety Population

The safety population will include all randomized subjects who receive at least 1 dose of the study drug, with subjects grouped according to the treatment they receive. This population will be used in all safety analyses with subjects analyzed according to the actual treatment they receive. If subjects receive a different treatment from the one they were randomized to throughout the entire study, they will be analyzed according to the different treatment received. However, subjects who receive mixed treatments due to dosing errors will be analyzed according to their randomized treatment.

2.4. Pharmacokinetic Population

The Pharmacokinetic (PK) population will be a subset of the safety population, which includes all randomized subjects who take at least 1 dose of the study drug and do not violate the protocol in a way that might affect the evaluation of the effect of the study drug(s) on the PK assessment (i.e., without major protocol violations or deviations). The subjects who receive placebo will be excluded from the PK population.

A separate documentation containing the final exclusion criteria and a list of subjects in this population will be finalized before the database lock for the double-blind treatment period and the treatment unblinding.

3. GENERAL CONSIDERATIONS

3.1. Definition of Estimand

The primary estimand of the study is intended to provide a population level estimate of treatment effect in terms of the change from baseline in blood tHTT protein at Month 3, by a hypothetical strategy. The primary analysis will be based on ITT population, aiming to answer the research question: what is the change from baseline in blood tHTT protein at Month 3 for all randomized subjects during their treatment period, defined as the time from randomization until 30 days after they stop the treatment. [Table 1](#) lists all estimands in the study.

Table 1: Study Endpoints and Estimands

Endpoint	Population	Variable	Intercurrent events	Population level summary	Analysis
Blood tHTT protein	Stage 2 and Mild Stage 3 HD subjects aged 25 years and older as defined by the protocol I/E criteria (ITT Population)	Change from baseline in blood tHTT protein at Month 3	Discontinuation of study treatment (due to any reason); data after the last dose of study drug + 30 days will be excluded.	Treatment difference and corresponding 95% confidence interval (CI) between each PTC518 dose group and placebo group in the change from baseline in blood tHTT protein at Month 3 will be estimated using a mixed model repeated measures (MMRM).	Primary analysis for primary endpoint
Blood tHTT protein	Stage 2 and Mild Stage 3 HD subjects aged 25 years and older as defined by the protocol I/E criteria, with no major protocol deviations which may affect treatment efficacy measurements (PP Population)	Change from baseline in blood tHTT protein at Month 3	Discontinuation of study treatment (due to any reason); data after the last dose of study drug + 30 days will be excluded.	Same as primary analysis for primary efficacy endpoint	Sensitivity analysis for primary endpoint
Blood tHTT protein	Stage 2 and Mild Stage 3 HD subjects aged 25 years and older as defined by the protocol I/E criteria (ITT Population)	Change from baseline in blood tHTT protein at Month 3 based on the results from	Discontinuation of study treatment (due to any reason); data after the last dose of study drug + 30 days will be excluded.	Same as primary analysis for primary efficacy endpoint	Sensitivity analysis for primary endpoint

PTC518-CNS-002-HD
Statistical Analysis Plan

Endpoint	Population	Variable	Intercurrent events	Population level summary	Analysis
		complete run (see definition in Section 5.2.3)			
Blood tHTT protein	Completers of Stage 2 and Mild Stage 3 HD subjects aged 25 years and older as defined by the protocol I/E criteria (ITT Population completers)	Change from baseline in blood tHTT protein at Month 3	Discontinuation of study treatment (due to any reason); data after the last dose of study drug + 30 days will be excluded.	Same as primary analysis for primary efficacy endpoint	Sensitivity analysis for primary endpoint
Blood tHTT protein	Stage 2 and Mild Stage 3 HD subjects aged 25 years and older as defined by the protocol I/E criteria (ITT Population)	Change from baseline in blood tHTT protein at Month 3	Discontinuation of study treatment (due to any reason); data after the last dose of study drug + 30 days will be excluded.	Treatment difference and corresponding 95% CI between each PTC518 dose group and placebo group in the change from baseline in blood tHTT protein at Month 3 will be estimated using a MMRM model, with missing data imputed using a control-based method.	Sensitivity analysis for primary endpoint
Caudate volume via vMRI	Stage 2 and Mild Stage 3 HD subjects aged 25 years and older as defined by the protocol I/E criteria (ITT Population)	Percent change from baseline in caudate volume as assessed via vMRI at Month 12	Discontinuation of study treatment (due to any reason); data after the last dose of study drug + 30 days will be excluded.	Treatment difference and corresponding 95% CI between each PTC518 dose group and placebo group in the percent change from baseline in caudate volume at Month 12 will be estimated using a MMRM model.	Analysis of key secondary endpoint
cUHDRS	Stage 2 and Mild Stage 3 HD subjects aged 25 years and older as defined by the protocol I/E criteria (ITT Population)	Change from baseline in cUHDRS scores at Month 12	Discontinuation of study treatment (due to any reason); data after the last dose of study drug + 30 days will be excluded.	Treatment difference and corresponding 95% CI between each PTC518 dose group and placebo group in the change from baseline in cUHDRS scores at Month 12 will be	Analysis of secondary endpoint

Endpoint	Population	Variable	Intercurrent events	Population level summary	Analysis
				estimated using an analysis of covariance (ANCOVA) model.	
Blood tHTT protein	Stage 2 and Mild Stage 3 HD subjects aged 25 years and older as defined by the protocol I/E criteria (ITT Population)	Change from baseline in blood tHTT protein at Month 12	Discontinuation of study treatment (due to any reason); data after the last dose of study drug + 30 days will be excluded.	Same as primary analysis for primary efficacy endpoint	Analysis of secondary endpoint
CSF mHTT protein	Stage 2 and Mild Stage 3 HD subjects aged 25 years and older as defined by the protocol I/E criteria; outliers will be excluded (ITT Population excluding outliers)	Change from baseline in CSF mHTT protein at Month 12	Discontinuation of study treatment (due to any reason); data after the last dose of study drug + 30 days will be excluded.	Same as primary analysis for primary efficacy endpoint	Analysis of secondary endpoint
CSF mHTT protein	Stage 2 and Mild Stage 3 HD subjects aged 25 years and older as defined by the protocol I/E criteria (ITT Population)	Change from baseline in CSF mHTT protein at Month 12	Discontinuation of study treatment (due to any reason); data after the last dose of study drug + 30 days will be excluded.	Same as primary analysis for primary efficacy endpoint	Sensitivity analysis of secondary endpoint
Blood mHTT protein	Stage 2 and Mild Stage 3 HD subjects aged 25 years and older as defined by the protocol I/E criteria (ITT Population)	Change from baseline in blood mHTT protein at Month 12	Discontinuation of study treatment (due to any reason); data after the last dose of study drug + 30 days will be excluded.	Same as primary analysis for primary efficacy endpoint	Analysis of secondary endpoint

